6.2.3 Suspected unexpected serious adverse reactions (SUSARs)

Not applicable.

6.3 Annual safety report

Not applicable.

6.4 Follow-up of adverse events

All AEs will be followed until they have abated, or until a stable situation has been reached. Depending on the event, follow up may require additional tests or medical procedures as indicated, and/or referral to the general physician or a medical specialist. SAEs need to be reported till end of study within the Netherlands, as defined in the protocol

6.5 [Data Safety Monitoring Board (DSMB) / Safety Committee]

The additional risk of the use of the Dual Mobility cups over and above the risks of standard care, are deemed to be negligible and therefore no DSMB will be established.

Version number: 7.0.,14-11-2023 17 of 26

7. STATISTICAL ANALYSIS

7.1 Primary study parameter(s)

The primary outcome, the difference in number of dislocations in both groups, will be analysed using the chi-square test. In case the assumptions of this test are not met, Fischer exact test will be applied. Multilevel logistic regression analysis will be used for analyses in which we adjust for clustering of data (e.g. at the hospital level), possible confounding and effect modification. A multilevel survival model will be used to analyse the survival of the implant, corrected for covariates.

The best way to handle missing values will be defined and applied for all analyses, including the cost-effectiveness analysis.

7.2 Secondary study parameter(s)

Secondary study parameters concern revision surgery, and patient reported physical functioning, quality of life, pain, satisfaction, fear of hip dislocation, healthcare and societal costs, device-related complications and reoperations. The secondary outcomes will be analysed using similar multilevel models as appropriate for each outcome (linear/logistic/survival).

Cost-effectiveness analysis

An economic evaluation will be performed from the societal perspective, for dislocation and Quality Adjusted Life Years (QALYs). Prevailing guidelines of Zorginstituut Nederland will be observed. All costs and consequences relevant to THA, hip dislocation and hip revision will be taken into account.

To compare costs between groups, confidence intervals around the mean differences in costs at one year after THA will estimated using the bias-corrected and accelerated bootstrap method. To account for possible clustering of data and to adjust for possible confounders, multilevel analyses will be performed. To graphically present the incremental cost-effectiveness ratios and uncertainty around them, bootstrapped cost-effect pairs will be plotted on cost-effectiveness planes. Cost-effectiveness acceptability curves will present the probability that the dual-mobility cup is more cost-effective than the unipolar cup for a range of willingness-to-pay thresholds. To study the robustness of these results, sensitivity analyses will be performed.

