3.4 Sample size calculation

Exact dislocation rates in the Netherlands are unknown. Based on previous studies and reviews, we assume that current dislocation rate for unipolar cups is 4% whereas DM cups result in 1% dislocation. $^{10;12;14;15;17;18;46}$ Power analysis indicates that a total sample of 976 (488 in each group) is needed to detect a difference in dislocations between 4% in the unipolar cup group and 1% in the dual-mobility cup group, using the chi-square test with 80% power and α =0.05. To account for loss to follow-up, 550 patients will be included in each group.

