5.1.3 Other study parameters (if applicable)

Covariates are:

- Sex
- Age
- ASA score
- BMI
- Brand cup
- Type of stem
- Type of anesthesia (general or spinal)
- Education level
- Awareness of type of cup that was placed

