5.3 Study procedures

During the pre-operative visit at the outpatient clinic, patients who are potential candidates for this study will be screened to determine if they meet the inclusion / exclusion criteria. If the patient is eligible, the investigator (or his designated representative) informs the patient about the study and proposes study participation, according to GCP guidelines. If desired, an additional telephone appointment can be arranged. Patients must sign an ethical committee (METC) approved study informed consent form (ICF) prior to participating in any study specific activities. The ICF can be signed face to face by the patient and investigator, or the patient can sign the ICF remotely and send it to the investigator by mail (due to COVID-19 restrictions). Subsequently, the investigator can sign the ICF and send one version to the patient. The ICF will be stored in a locked closet in the participating center. Pre-operative data will be collected including: demographics and medical history, NRS for pain in rest and during weight bearing, HOOS-PS and EQ-5D. The patients are also asked to fill out questionnaires. See table 1 for an overview of all measurements and follow-up moments.

Evaluation moment	Pre-operative	Intra-operative	3 months	1 year	2 years
Preoperative data (screening)	х				
Surgical Details		х			
PROMs	х		х	х	х
Serious Adverse Events	Anytime				

Table 1: Overview of follow-up moments.

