7.4 Interim analysis (if applicable)

Interim analyses for the primary study outcome will be performed when 200 patients have reached the 3 months postoperative PROM evaluation point. In the interim analyses the number of dislocations in each group will be compared. A chi-square test will be used and in case the assumptions of this test are not met, Fischer exact test will be applied. To guard against a type 1 error, we use the O'Brien-Fleming approach. As only one interim analysis will be performed, the alpha for this analysis is set at 0.005. Testing will be done two-sided. Furthermore, we will take the number of revisions and SAE's in each group in consideration, but will not formally test for differences in these. Results of the interim analysis will be discussed with the steering committee, Van Rens Foundation and the ethical committee. In case of a statically significant and relevant higher number of dislocations in the DM group, or more revisions or SAE's, appropriate actions will be taken (such as an early termination of the study).

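### The covariate list omits the pre-operative HOOS-PS, EQ-5D and NRS pain scores although they are collected, which costs precision in the PROM and QALY comparisons

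*Protocol*

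**What the plan says.** Section 5.3 (Study procedures) has the scores measured before surgery: "Pre-operative data will be collected including: demographics and medical history, NRS for pain in rest and during weight bearing, HOOS-PS and EQ-5D". Section 5.1.2 places the PROMs pre-operatively, at 3 months and at 1 year, with one more measurement at 2 years for this study.

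Section 5.1.3 opens its list with "Covariates are" and names nine variables: sex, age, ASA score, BMI, cup brand, stem type, type of anaesthesia, education level and awareness of the cup type. No pre-operative PROM or EQ-5D score is among them. The last item, awareness, is asked only at the follow-up moments (5.1.2), so the list holds a post-randomisation variable but not the baseline value of the outcome.

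For the PROMs, section 7.2 says: "The secondary outcomes will be analysed using similar multilevel models as appropriate for each outcome (linear/logistic/survival"). For the economic evaluation, with QALYs as one of its effects, 7.2 provides multilevel analyses that allow for clustering and adjust for confounders that it does not name. Neither statement mentions a baseline term, and neither excludes one.

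**The concern.** The pre-operative value of a score is usually among the best predictors of its later value. Leaving it out of the model puts explainable variation into the residual and widens the confidence interval. The only covariate list in the protocol omits it.

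The matter is sharper for QALYs. EQ-5D before surgery, at 3 months and at 1 year would normally be turned into an area under the curve. The pre-operative score then enters the QALY itself and also predicts the two later scores. The expected QALY difference is small, because only a few patients per hundred are expected to be spared a dislocation. Noise from the baseline score can therefore be of the same order as the effect. The cost-effectiveness planes and acceptability curves in 7.2 depend on that difference.

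If the term is not named in advance, whether to adjust may be decided after the baseline table has been seen.

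**Working it through.** **Inputs from the protocol**
- Rates (3.4): "we assume that current dislocation rate for unipolar cups is 4% whereas DM cups result in 1% dislocation", a difference of 0.03.
- Design (3.4): "using the chi-square test with 80% power and α =0.05". Two-sided testing is stated only for the interim analysis (7.4).
- Size (3.4): "Power analysis indicates that a total sample of 976 (488 in each group) is needed".
- PROM times within the 1-year horizon (5.1.2): 0, 3 and 12 months.

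**Assumptions (not in the protocol)**
- Baseline–follow-up correlation r: 0.2 to 0.5.
- Pre-operative EQ-5D standard deviation (SD): 0.15 to 0.30.
- Follow-up EQ-5D SD: 0.20, with correlation 0.6 between the two follow-up scores.
- QALYs by the trapezoid rule.
- QALY loss per patient with a dislocation: 0.05 to 0.30.

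**Step 1. The plan's own figure.** The two-proportion formula for 4% against 1%, two-sided 5%, 80% power:
- Without continuity correction: n = [1.96·√(2·0.025·0.975) + 0.842·√(0.04·0.96 + 0.01·0.99)]² / 0.03² = 424 per arm.
- With continuity correction: (424/4)·[1 + √(1 + 4/(424·0.03))]² ≈ 488.4, or 489 when rounded up.

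The stated 488 is reproduced to within rounding. It concerns the primary outcome only. The protocol gives no sample size, SD or expected difference for PROMs or QALYs. 488 per arm is used below.

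**Step 2. A single PROM follow-up score.** Adjustment multiplies the standard error (SE) by √(1 − r²). The equivalent gain in sample size is 1/(1 − r²) − 1.

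| r | SE factor | SE reduction | Equivalent extra patients |
|---|---|---|---|
| 0.3 | √0.91 = 0.954 | 5% | 10% |
| 0.5 | √0.75 = 0.866 | 13% | 33% |

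**Step 3. QALY weights.** Over 0, 0.25 and 1 year the trapezoid weights are 0.25/2 = 0.125, (0.25 + 0.75)/2 = 0.5 and 0.75/2 = 0.375.

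**Step 4. SE of the QALY difference.** Worked case with pre-operative SD 0.25 and r = 0.3:
- Variance of one patient's QALY = 0.000977 + 0.01 + 0.005625 + 0.001875 + 0.001406 + 0.009 = 0.02888 (three variance terms, then three covariance terms).
- Unadjusted SE = √(2·0.02888/488) = 0.0109.
- Covariance with baseline = 0.125·0.0625 + (0.5 + 0.375)·0.3·0.25·0.20 = 0.02094. Slope = 0.02094/0.0625 = 0.335.
- Adjusted variance = 0.02888 − 0.02094²/0.0625 = 0.02187. Adjusted SE = √(2·0.02187/488) = 0.0095, a reduction of 13%.

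Over the full assumed ranges, the SE falls from 0.0104–0.0116 to 0.0083–0.0098, a reduction of about 6 to 28%.

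**Step 5. What a chance baseline imbalance does to the unadjusted difference.**
- SE of the baseline difference = SD·√(2/488), which is 0.010 at SD 0.15, 0.016 at 0.25 and 0.019 at 0.30.
- Shift for a 1-SE imbalance = slope × that SE. This gives 0.003 to 0.008 over the ranges above.
- If the SD is instead 0.25 both before and after surgery, the shift is 0.016·(0.125 + 0.875·r): 0.0062 at r = 0.3 and 0.0090 at r = 0.5.
- Taken together: about 0.003 to 0.009. The direct weight of the baseline score alone (0.125) accounts for only 0.0012 to 0.0024.

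**Step 6. Against the expected difference, 0.03 × QALY loss per patient with a dislocation.**

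| Assumed loss | Expected difference | Against a 1-SE shift of 0.003–0.009 |
|---|---|---|
| 0.05 | 0.0015 | shift is larger |
| 0.10 | 0.003 | shift equals or exceeds it |
| 0.20 | 0.006 | similar size |
| 0.30 | 0.009 | shift does not exceed it |

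The adjusted SE of 0.008–0.010 is itself above the expected difference for losses up to about 0.25 QALY (0.03·0.25 = 0.0075).

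**The case against.** The strongest reply is that the protocol does not exclude the baseline score. Section 7.2 leaves the model to suit each outcome and lets the economic evaluation adjust for confounders. A multilevel model could also carry the pre-operative score as a repeated measure. Section 5.1.3 stands under other study parameters, is not tied to the PROM or QALY models and is not called exhaustive. A statistical analysis plan that is not shown may settle the matter. This stands: a reader might infer that the protocol has decided to analyse PROMs and QALYs without baseline, and the text does not support that. What remains is that the one explicit list omits the score and nothing requires it.

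A reader might also infer that baseline imbalance will swamp the QALY result, or decide its sign, unless it is adjusted for. That goes too far for three reasons:
- It rests on an SD, a correlation and a QALY loss that the protocol does not give, and it fails at losses of about 0.3 QALY.
- Under randomisation, chance imbalance is not bias and is already inside the unadjusted interval. It is the same point as the lost precision and should not be counted twice.
- Adjustment would not cure it. At a true difference of 0.003, even the largest fall in SE (0.0116 to 0.0083) lowers the chance of a wrong sign only from about 40% to 36% (normal approximation). At 0.006 it falls from about 30% to 23%.

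The small expected effect is the main reason that the QALY comparison is imprecise.

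**Conclusion.** The point holds as one about precision in secondary analyses. The list in 5.1.3 omits scores that 5.3 collects, and following it as written makes the intervals wider than necessary. Adjustment shortens the SE by about 5 to 13% for a PROM (assumed r of 0.3 to 0.5) and by about 6 to 28% for the QALY difference at 488 per arm (assumed SDs and correlations as listed). A 1-SE chance imbalance in baseline EQ-5D can move the unadjusted QALY difference by about 0.003 to 0.009. That can equal or exceed the expected difference if a dislocation costs about 0.1 QALY or less, but does not exceed it at about 0.3 or more.

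The documents do not support a claim of bias, or a claim that adjustment would make the cost-utility result precise. The primary outcome, its sample size and the interim analysis are untouched.

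**What to change.** In 5.1.3, add the pre-operative HOOS-PS, EQ-5D and NRS pain scores (at rest and during weight bearing) to the covariates. In 7.2, state that each PROM model includes the pre-operative value of that same PROM. State also that the model for incremental QALYs adjusts for pre-operative EQ-5D utility and that this adjustment is repeated within each bootstrap sample. If a separate analysis plan already specifies this, bring the protocol list into line with it.

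The cost is one covariate per model and two sentences of text. No new data, visits or patients are needed. The change should be made before outcome data are compared by arm, so that it cannot depend on the imbalance observed.

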7.3 Other study parameters

A priori subgroup analysis

We will analyse patient's characteristics known for influencing dislocation rate.

These include:

- Gender
- Age
- ASA classification
- Femoral head avascular necrosis
- Acute Fracture
- Late posttraumatic condition of the hip

We trust randomization to balance these confounders in both treatment and intervention group.

7.4 Interim analysis (if applicable)

Interim analyses for the primary study outcome will be performed when 200 patients have reached the 3 months postoperative PROM evaluation point. In the interim analyses the number of dislocations in each group will be compared. A chi-square test will be used and in case the assumptions of this test are not met, Fischer exact test will be applied. To guard against a type 1 error, we use the O'Brien-Fleming approach. As only one interim analysis will be performed, the alpha for this analysis is set at 0.005. Testing will be done two-sided. Furthermore, we will take the number of revisions and SAE's in each group in consideration, but will not formally test for differences in these. Results of the interim analysis will be discussed with the steering committee, Van Rens Foundation and the ethical committee. In case of a statically significant and relevant higher number of dislocations in the DM group, or more revisions or SAE's, appropriate actions will be taken (such as an early termination of the study).

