5.7 Premature termination of the study

Because the devices used in this study are CE marked and will be used according to its labeling, there are no preconceived reasons for premature termination of the study. Upon the sponsor / principal investigator's decision to terminate or suspend the study, the involved parties and METC will be notified promptly, stating the reasons.

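### Section 7.4 sets the interim alpha at 0.005 as the O'Brien-Fleming value, but that value belongs to a look at half the information, and the planned look comes at 20% or less

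*Protocol*

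**What the plan says.** Protocol section 7.4 plans one interim comparison of dislocations between the groups, "when 200 patients have reached the 3 months postoperative PROM evaluation point". The test is chi-square, with Fisher's exact test as the fallback. On error control it says "To guard against a type 1 error, we use the O'Brien-Fleming approach", and it derives the level from the number of looks: "As only one interim analysis will be performed, the alpha for this analysis is set at 0.005". It adds "Testing will be done two-sided".

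The action it then describes goes one way. If the DM group has significantly and relevantly more dislocations, or more revisions or SAEs, appropriate steps follow, of which early termination is given as an example. Nothing is said about what follows a significant result in favour of DM.

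Section 7.4 gives no information fraction and no final level, and section 7.1 gives no level for the primary test. The only other alpha in the protocol is in section 3.4, where the sample size is computed "using the chi-square test with 80% power and α =0.05".

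**The concern.** O'Brien-Fleming boundaries are very strict early and relax as information accrues. The interim level therefore depends on when the look happens, and having only one look does not make it 0.005. At a look this early, 0.005 is far more permissive than the method named. The level and the method cannot both govern the interim decision, and a reader cannot tell which one does.

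Two further gaps follow. A look at 0.005 that can stop the trial in either direction calls for a reduced final level, and none is given. A two-sided test whose only consequence lies in one direction also leaves open whether the look is a formal efficacy look or a safety look. The interim decision rule and the final significance level depend on that answer.

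**Working it through.** **Inputs.** From the protocol: 976 evaluable patients, 488 per group, with risks of 4% and 1% (section 3.4); 1100 randomised (section 5.2); 200 patients at 3 months and interim alpha 0.005 two-sided (section 7.4); primary endpoint at 1 year (section 1); about half of first-year dislocations within three months (Introduction). Assumed: equal allocation at the look, so about 100 per group.

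**1. The plan's own sample size.** Chi-square, two-sided 0.05, 80% power, pooled variance, p̄ = 0.025:

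n = [1.960·√(2·0.025·0.975) + 0.842·√(0.04·0.96 + 0.01·0.99)]² / 0.03² = 424 per group.

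With continuity correction: (n/4)·[1 + √(1 + 4/(n·0.03))]² = 488.4, against 488 stated. The figure reproduces at the full two-sided 0.05, with nothing deducted for an interim look.

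**2. Information fraction t.**
- By patients: 200/1100 = 0.182; 200/976 = 0.205.
- By events: expected first-year events are 976 × 0.025 = 24.4. At the look, 200 × 0.025 × 0.5 = 2.5. So t ≈ 2.5/24.4 = 0.10. Some patients will have been followed beyond 3 months, so this is approximate.

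**3. O'Brien-Fleming levels.** The two test statistics are bivariate normal with correlation √t. Reject at the look if |Z1| > c/√t and at the end if |Z2| > c, with c solved for an overall 0.05.

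| t | c | interim level (two-sided) | final level |
|---|---|---|---|
| 0.50 | 1.977 | 0.0052 | 0.0480 |
| 0.205 | 1.960 | 0.000015 | 0.0500 |
| 0.182 | 1.960 | 0.000004 | 0.0500 |
| 0.10 | 1.960 | below 0.000000001 | 0.0500 |

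The stated 0.005 matches only the first row. Against the second it is 0.005/0.000015 ≈ 330 times too large. Two-sided Lan-DeMets spending of the O'Brien-Fleming type gives the same interim values at t = 0.205 and 0.182, so that version does not rescue 0.005.

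**4. Nominal overall error if 0.005 is paired with a final 0.05.** The critical values are 2.807 and 1.960.

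| t | stop in either direction | stop for harm only |
|---|---|---|
| 0.205 | 0.0537 | 0.0518 |
| 0.182 | 0.0538 | 0.0519 |
| 0.10 | 0.0542 | 0.0521 |

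The bound for any t is 0.05 + 0.005 = 0.055. With harm-only stopping, the excess lies wholly in the tail that says DM is worse; the chance of falsely claiming DM benefit stays at or below 0.025.

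**5. The test that would actually be used.** Expected events per group at the look are about 100 × 0.0125 = 1.25, well under 5, so the Fisher fallback applies. At 100 per group, 8 versus 0 gives p = 0.0068 and 9 versus 0 gives p = 0.0032, so at least 9 versus 0 is needed. The exact null probability of crossing 0.005, by 3-month risk, is:
- 1.25%: 0.000003
- 2%: 0.00005
- 3%: 0.0004

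In simulation under the null (1-year risk 2.5% or 4%, half by 3 months), the look crosses in fewer than 1 in 10,000 trials and the overall error is about 0.050. At a 1-year risk of 1% it is 0.043.

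**The case against.** A reader might infer that type I error control fails. The documents do not support that, for four reasons.

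- **The final level is not stated.** That it stays at 0.05 is inferred from the power calculation in section 3.4. A SAP, not shown here, may set it.
- **An unreduced 0.05 is not itself the fault.** Under a true O'Brien-Fleming boundary this early, a final level of about 0.05 is right. The fault is the 0.005 and the reason given for it.
- **Section 7.4 does not describe symmetric stopping.** The totals of 0.0537 to 0.0542 need a stop for benefit as well as harm. A two-sided 0.005 acted on in one direction puts 0.0025 in that tail, and the action is discretionary.
- **The specified test spends almost no alpha.** With so few events, Fisher's exact test is very conservative. Cutting the final level to about 0.046, the normal-theory correction, would cost power to repair an inflation that this test does not produce.

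A reader might also see section 5.7 ("there are no preconceived reasons for premature termination of the study") as contradicting the early termination mentioned in 7.4. That is weak: 5.7 ties its statement to the devices being CE marked and itself allows the sponsor to terminate, and 6.1 provides for suspension on safety grounds. A contingent harm look is compatible with both.

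All of this stands, and it limits the size of the point. It does not make the sentence in 7.4 correct: the protocol itself states the method, the level and the reason, and a SAP could supply a final level without making those three agree.

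**Conclusion.** The point holds as a mismatch between the named method, the stated level and the timing. The value 0.005 is the O'Brien-Fleming level at half the information. At 18% to 20% of patients it would be about 0.000004 to 0.000015, and lower still by events. The direction in which the look can act and the final level are not settled in the protocol.

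The consequence for error control is small: nominally at most about 0.054, about 0.052 with harm-only stopping and no increase in false claims of DM benefit, and about 0.050 with Fisher's exact test. These figures assume equal allocation at the look, about half of first-year events by three months, and a final test at 0.05. Severity is minor to moderate: a decision threshold is wrongly justified and should be corrected, but the validity of the primary result is not in doubt on this account.

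**What to change.** Amend section 7.4 in one of two ways.

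1. **Describe a harm-only safety look.** Keep 0.005 as a non-binding guide, drop the O'Brien-Fleming claim and the reason based on the number of looks, state that there is no stopping for benefit, and state a final two-sided level of 0.05. This is closest to what 7.4 already describes.
2. **Keep O'Brien-Fleming.** State the information fraction and how it is measured (patients or events), use a Lan-DeMets boundary at the actual fraction, say which directions can stop the trial, and give a final level of about 0.05. Such a boundary would be very hard to cross with about 100 per group: even 11 versus 0 gives p = 0.0007, some 49 times 0.000015. The look would then rest almost wholly on judgement.

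Either way the cost is protocol wording. The final level stays at about 0.05, so the sample size of 488 per group is unaffected.
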